### ***Adverse events***

An **adverse event** (AE) is the development of an undesirable medical condition or the deterioration of a pre-existing medical condition following or during exposure to a pharmaceutical product, whether or not

considered causally related to the product. An undesirable medical condition can be symptoms (e.g., nausea, chest pain), signs (e.g., tachycardia, enlarged liver) or the abnormal results of an investigation (e.g., laboratory findings). In clinical studies, an AE can include an undesirable medical condition occurring at any time, including run-in or wash-out periods, even if no study treatment has been administered.

A **serious adverse event (SAE)** is an AE occurring during any study period (i.e., run-in, treatment, wash-out, follow-up), and at any dose of the investigational product, comparator or placebo, that fulfils one or more of the following criteria:

- results in death
- is immediately life-threatening
- requires in-patient hospitalisation or prolongation of existing hospitalisation
- results in persistent or significant disability or incapacity
- is a congenital anomaly or birth defect
- is an important medical event that may jeopardise the patient or may require medical intervention to prevent one of the outcomes listed above

A distinction should be drawn between serious and severe events. A severe event is a major event of its type. The term “severe” is used to indicate the intensity of a specific event, while the term “serious” is based on patient/event outcome or action criteria.

A **suspected unexpected serious adverse reaction (SUSAR)** is any adverse event with a reasonable possibility of a link to the study drug that is both serious and unexpected (i.e. not consistent with the information about the study drug in either the SPC or IB).

### **Procedures for Serious Adverse Event Reporting**

An SAE form should be completed and faxed to the Trial Manager/Chief Investigator for all SAEs (or AESIs) within 24 hours. The Trial Manager/Chief Investigator should inform the sponsor of all SAEs within 24 hours of receiving notice. All SAEs should be recorded on the annual safety reports that are sent to the MHRA and REC on the anniversary of the date a favourable opinion for the study was given.

Contact details for reporting SAEs and SUSARs [contact], attention [name] Please send SAE forms to: [name] [contact] (Mon to Fri 09.00 – 17.00)

Contact details for reporting SAEs and SUSARs to the Sponsor [contact]

### **SUSAR reporting**

Expedite Reporting will be performed by the Principal Investigator in case of any suspected, unexpected, serious adverse reaction (SUSAR) or in case of other safety issues that qualify for expedite reporting, in accordance with the European Directive 2001/20/EC. In the case of suspected unexpected serious adverse reactions, the staff at the site should:

Complete the SAE case report form & send it immediately (within 24 hours, preferably by fax), signed and dated to the study coordination centre together with relevant treatment forms and anonymised copies of all relevant investigations.

Or

Contact the study coordination centre and/or the CI as above by phone and then send the completed SAE form to the study coordination centre within the following 24 hours as above.

The study coordination centre will notify the MHRA, REC and the Sponsor of all SUSARs occurring during the study according to the following timelines; fatal and life-threatening within 7 days of notification and non-life threatening within 15 days. All investigators will be informed of all SUSARs occurring throughout the study.

The expedite reporting to the Competent Authority and Ethics Committee will be performed as follows:

- fatal or life-threatening SUSAR, will be reported as soon as possible but no later than 7 calendar days after first knowledge of the minimum criteria for expediting reporting. Relevant follow-up information will be completed as soon as possible and sent within an additional 8 calendar days.
- non fatal or life-threatening SUSAR, will be reported as soon as possible but no later than 15 calendar days after first knowledge of the minimum criteria for expediting reporting.

### **SUSAR and SAE reporting**

Copy of SAE/SUSAR reporting will be notified by the Principal Investigator to the Sponsor's Representative at Imperial College Joint Research Compliance Office (JRCO) within 24 hrs of becoming aware of the event.

### **Data Handling and Record Keeping**

Hard copies of participant's trial research files will be kept under lock and key in the RBH Respiratory BRU CRF. Access to these will be limited to the Respiratory Physician conducting the study ([name]), the Co-Investigator ([name]) and the Clinical Research Nurse ([name]). All files will have non identifiable information, that is, each participant will only be identified by a study code and the study codes for each participant will be kept in a separate locked cabinet.

The Investigators will permit trial-related monitoring, audits, IRB/IEC reviews and internal and external regulatory inspection with provision and direct access to source documents and data. The following has been included in the Patient Information Sheet to patients;

It will be the responsibility of the Chief Investigator and Consultant Respiratory Physician conducting the study – [name], to ensure the well-being of all participants and that they are able to contact him for any queries regarding the study. [name] & [name] will also be responsible for the daily management and monitoring of the research data and management of the staff involved with the research.

[name] & [name] will liaise with the clinical research governance office at Imperial College with respect to auditing the research study.

Overall responsibility for the study lies with the Chief Investigator, [name], Clinical Senior Lecturer and Honorary Consultant in Respiratory Medicine, National Heart and Lung Institute, Imperial College. The project will be registered with the Clinical Research Office of Imperial College London and on [ClinicalTrials.gov](http://ClinicalTrials.gov).

### **Indemnity**

Indemnity will be provided by Imperial College Indemnity Scheme which has been arranged through the Clinical Research Office at Imperial College. Public Liability cover is also provided for Imperial College under this policy reference number.

## Publication

It is hoped that the results and data from the research will be available publicly in peer-reviewed publications. Although no specific publications will be produced for the research participants, should a participant request feedback on the outcome of research towards which they have contributed, this will be provided to them. Information about publication arrangements will be included in the participant information sheet, as well as a statement regarding information on individual requests for feedback on the study results.

## 16. STUDY COSTS

PERSONNEL (ICL)	
STUDY	
PHARMACY (RBH)	
	-set-up
	-IMP management fee/month
	-dispensation inc. reconciliation
	-DRUG COSTS
RBH CRF COSTS	- room use
R&D (RBH)	-set-up
	-per patient RBH Trust
INFORM DATA MANAGEMENT	
	Design, development and documentation of e-CRF with monitor/audit in place
PATIENTS (ICL)	
	patient inc travel, food and inconvenience
EQUIPMENT SMALL AIRWAYS & SERVICE (ICL)	
	IOS and MBNW / annum
CONFERENCE	
	Support to either ERS or ATS inclusive of economy travel, registration, hotel

- ***Statistical support will be given by Boehringer Ingelheim***
- ***Placebo inhalers Handihaler and Respimat will be supplied by Boehringer Ingelheim***

Principal Investigator: [name]

Imperial's Ref No: P53611

Study Budget	GBP
STAFF COSTS (salary & on-costs)	

PI	£39,658.11
Researcher (adjust start date June 1 st 2015)	£179,526.97
DIRECT STUDY CONSUMABLES	
Patient volunteer payments	£12,740.69
Consumables	£2,919.15
Pharmacy costs	£6,024.36
Drug costs	XXXX
R&D costs	£6,625.16
BRU(Biomedical Research Unit) costs (room hire)	XXXX
Travel costs	£2,038.51
InForm costs	£21,842.80
FACILITIES & EQUIPMENT	
Access charges	£34,503.47
Infrastructure costs	£8,972.65
TOTAL	£314,851.87

Study Protocol Version 6 (01/09/16)

**TARGETING OF THE SMALL AIRWAYS IN PATIENTS WITH COPD: AIRWAY EFFECTS OF
TIOTROPIUM – Respimat vs. Handihaler**

NCT02683668

STATISTICAL ANALYSES

Study Protocol Version 6 (01/09/16)

TARGETING OF THE SMALL AIRWAYS IN PATIENTS WITH COPD: AIRWAY EFFECTS OF TIOTROPIUM – Respimat vs. Handihaler

EudraCT No: 2015-001615-13

REC/IRAS number: 15/LO/0982

Sample Size Calculation

The primary endpoint is the Impulse oscillometry measure of IOS R5-R20.

Each subject will act as their own control and assuming the treatment effect (ie the difference R5-R20 between baseline and 14 days) to be 0.03kPa(L/s) with an SD of 0.05, then 44 subjects will be required to achieve the said treatment effect at 1% significance and 90% power.

Statistical Analysis

t-tests/Mann-Whitney tests and linear mixed models will be used to measure overall treatment effect while adjusting for baseline variables.

The secondary endpoints are small airways (MBNW, DLCO, FVC) and large airways (FEV1, PEF) airways physiology and also the CAT score.

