## **2. QUESTIONS THIS STUDY WILL ANSWER**

PHASE 1: Effect of Inhaler Training with Handihaler on airway function and symptoms

If we train patients with the Handihaler properly can we

- improve (i) lung function (large and small airway)?
- improve(ii) clinical symptoms (determined by CAT score)?

Mild-moderate COPD [GOLD], established (>1 month) already on HandiHaler- Tiotropium 18 mcg once daily but have ongoing symptoms or exercise limitation (determined by CAT score) to be eligible to enter. So their clinical state may be due to 'real-life' poor inhaler technique (which will be assessed by the research observer). Patients receiving Handihaler who have not been trained for over 3 months on its use will be recruited.

We will train patients in the optimal use of the Handihaler.

So if we train patients with the Handihaler properly can we improve (i) lung function (large and small airway) and (ii) clinical symptoms (determined by CAT score).

Data comparison: Data from Visit 1 will be compared to the Screening Visit data.

PHASE 2: Is the device important in treating the small airways

- Does changing the device from a DPI-Handihaler (in a trained patient) to a SMI-Respimat give an added advantage to the patient? (keeping the dose of the drug equivalent from each device – that is Tio 18mcg HH = Tio 5mcg Resp).
- That is – is there an added advantage with the device that is observed with a change (improvement) in (i) lung function (large and small airway) and (ii) clinical symptoms (determined by CAT score).

- Do the properties of the Respimat device with deeper lung deposition (slow velocity and small particles) can improve small airway measures (and indeed large airway measures) that might also be related to an improvement in symptoms.

Data comparison: Data from Visit 2 will be compared to the Visit 1 data.

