### **3 . RESEARCH AIM & HYPOTHESIS**

We aim to investigate the effect of tiotropium from different devices on a panel of small (IOS, MBNW, DLCO, FVC) and large airway (FEV1, PEF) responses in patients with mild-moderate COPD. We will compare Tiotropium Handihaler 18 micrograms once daily with Tiotropium Respimat 5 micrograms once daily.

We will identify a COPD cohort with ongoing symptoms or exercise limitation on HandiHaler, as proposed. The science behind this is why are people still limited (even if partially as determined using the CAT score) and could it be that relatively we need more distal airway targeting (this doesn't necessarily mean acinar/alveolar beyond the terminal bronchioles, but just a little bit more going deeper into the distal conducting airway) that can be achieved with Respimat.

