### **4. STUDY DESIGN:** (also see **study treatment dosing flowchart below**)

**Target population: N=44 mild COPD patients.**

Open (as patients can identify inhaler device), Sequential, 3 visits (including screening visit).

Patients on concurrent oral bronchodilators (theophylline, PDE4 inhibitors) will not be included. Patients on concurrent LABAs will be allowed.

**N=44 Patients:** Mild-moderate COPD [GOLD], established (>1 month) already on HandiHaler- Tiotropium 18 mcg once daily **but have ongoing symptoms or exercise limitation (determined by CAT score)**

There will be three phases.

- **Phase 0** (Screening visit)  
Patients receiving Handihaler who have not been trained (real-life use) for over 3 months on its use
- **Phase 1**  
Patients will be trained in their use of Handihaler-Tiotropium and asked to take 18 mcg once daily for 14 days to see if their (i) airway lung function and or (ii) clinical symptoms improve AND THEN
- **Phase 2**  
Patients will be switched to trained Respimat Tiotropium 5 mcg once daily for 14 days to see if their (i) airway lung function and or (ii) clinical symptoms improve.

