#### **WHAT HAPPENS AT EACH VISIT?**

##### **(i) Phase 0 - SCREENING VISIT: (DAY 0)**

- IDENTIFY : Mild-moderate COPD [G.O.L.D], established (>1 month) already on HandiHaler- Tiotropium 18 mcg once daily but have ongoing symptoms or exercise limitation (determined by CAT score) to be eligible to enter
- Patient to avoid short acting SABA and SAMA and LABA on day of visit

- 9am Baseline: Lung physiology measurements undertaken in this order; IOS, MBNW, Spirometry (FVC) /Body plethysmography (DLCO).
- Patient asked to demonstrate how they use Handihaler with a demonstration device. Research observer notes how patient takes Handihaler-Tiotropium to assess good or poor inhalation technique /errors.
- Patient receives training in how to use Handihaler correctly until observer satisfied.
- 10am Patient takes Handihaler-Tiotropium 18 mcg od in Lab. Research observer notes how patient takes Handihaler-Tiotropium.
- 3hours post dosing: Lung physiology measurements undertaken in this order; IOS, MBNW, Spirometry (FVC) /Body plethysmography (DLCO).

Tests:

- Small (IOS, MBNW, DLCO, FVC) airways (these will be done on physiology machines of [name])
- Large (FEV1, PEF) airways (these will be done on physiology machines of [name])
- CAT score

**AIM OF THIS PHASE (0) OF STUDY:** Here we want to see that if patients have ongoing symptoms but are on Handihaler-Tiotropium what is happening PRIOR to proper inhaler technique training – that is their ‘real-life’ use of the inhaler - to their lung function (large and small airways) and also symptoms or exercise limitation (determined by CAT score) will already be recorded as entry criteria

- Patient will be asked to take Handihaler-Tiotropium 18 mcg od at 10am every day for 14 days

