**The primary endpoint is the Impulse oscillometry measure of IOS R5-R20.**

**Each subject will act as their own control and assuming the treatment effect (ie the difference R5-R20 between baseline and 14 days) to be 0.03kPa(L/s) with an SD of 0.05, then 44 subjects will be required to achieve the treatment effect at 1% significance and 90% power.**

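### The SAP names an independent-samples rank test for a one-cohort, within-patient design and does not say which visit comparison is primary

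*SAP*

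**What the plan says.** Protocol section 4 describes the design as "Open (as patients can identify inhaler device), Sequential, 3 visits (including screening visit"). All patients follow the same sequence: usual HandiHaler use, then trained HandiHaler for 14 days, then Respimat for 14 days. There is no parallel group.

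Protocol section 2 sets two comparisons. For training, "Data from Visit 1 will be compared to the Screening Visit data". For device, "Data from Visit 2 will be compared to the Visit 1 data". The aim in section 3 is the device question: "We will compare Tiotropium Handihaler 18 micrograms once daily with Tiotropium Respimat 5 micrograms once daily".

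Protocol section 10 and the SAP size the trial on the same basis. "Each subject will act as their own control", and the effect is "the difference R5-R20 between baseline and 14 days", taken as 0.03 with an SD of 0.05, giving 44 subjects at 1% significance and 90% power. Sidedness is not stated.

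The SAP's Statistical Analysis section then gives its only sentence on method: "t-tests/Mann-Whitney tests and linear mixed models will be used to measure overall treatment effect while adjusting for baseline variables". The analysis paragraph in Protocol section 10 lists the secondary endpoints and names no test.

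**The concern.** There are two gaps.

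**The test.** Both planned comparisons are between visits in the same patients, so there are no independent groups for Mann-Whitney to compare. The rank test that matches the design is the Wilcoxon signed-rank test, and it is not named. An analyst who follows the SAP literally would discard the pairing on which 44 patients rest.

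**The contrast.** The SAP speaks of one overall effect, while the protocol asks two questions. If the primary contrast is not named beforehand, the single 1% test could be attached to training or to device once the data are known.

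**Working it through.** **1. Reproduce N = 44.** Inputs from Protocol section 10 and the SAP: mean difference 0.03, SD 0.05, alpha 0.01, power 0.90.

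- Paired, normal approximation, two-sided: n = ((2.576 + 1.282) × 0.05/0.03)² = 41.3, so 42.
- Paired, exact noncentral t, two-sided: n = 45. At n = 44 the noncentrality is (0.03/0.05) × √44 = 3.98, the critical value is 2.695 (43 df), and power is 0.894.
- One-sided: 37 (normal) or 39 (exact t), with power 0.937 at n = 44.
- Two independent groups with SD 0.05: 83 per group two-sided, 73 one-sided.

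So 44 is a within-patient figure and fits a two-sided test best. Two-sided is assumed below.

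**2. What ignoring the pairing costs.** The documents give neither a between-visit correlation ρ nor a per-visit SD, so ρ is an assumption. Holding the SD of the difference at 0.05, the per-visit SD is 0.05/√(2(1−ρ)). An unpaired test uses a standard error that is too large by the factor 1/√(1−ρ). For an unpaired t-test (critical value 2.634, 86 df), power is therefore roughly Φ(3.98 − 2.634/√(1−ρ)). This gives 0.91, 0.80, 0.60 and 0.20 at ρ = 0, 0.3, 0.5 and 0.7. Simulation with normal data, 20,000 trials per setting, gives for Mann-Whitney:

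| Assumed ρ | Per-visit SD | Mann-Whitney power | Mann-Whitney rejection rate, no effect (nominal 0.01) |
|---|---|---|---|
| 0 | 0.035 | 0.887 | 0.0097 |
| 0.3 | 0.042 | 0.755 | 0.0024 |
| 0.5 | 0.050 | 0.561 | 0.0005 |
| 0.7 | 0.065 | 0.203 | 0.0000 |

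In the same simulations the paired t-test stays at 0.89 to 0.90 and the signed-rank test at 0.87 to 0.88. The error lowers power and does not add false positives.

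**3. Which contrast?** Protocol section 4 labels Screening as Day 0, Visit 1 as Day 14 and Visit 2 as Day 28. By those labels, the baseline-to-14-days wording of the sample size means Visit 1 against Screening, the training question. The title and aim point to Visit 2 against Visit 1, the device question. That phase also lasts 14 days, and section 4 calls the 9am tests baseline at both Screening and Visit 1. No sentence settles it. If a claim could be made on either comparison at 1%, the Bonferroni bound on the false-positive rate is 0.01 + 0.01 = 0.02.

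**4. Which time point?** Under section 4 the 3-hour values do not give a clean comparison for either contrast.

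- At Screening, before the in-lab dose, "Patient receives training in how to use Handihaler correctly until observer satisfied", so the 3-hour test already follows training.
- At Visit 1 the 3-hour test follows the first Respimat dose.
- At Visit 2 tests are listed at 9am and 10am only.

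Section 8, however, justifies the 3-hour measurement as the maximal response. It also gives a daily dosing time (ideally 9am) that differs from the 10am in section 4.

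**5. Would a random intercept be enough?** Not necessarily. Take equal variances σ² and assumed correlations of 0.5 (Screening–Visit 1), 0.8 (Visit 1–Visit 2) and 0.5 (Screening–Visit 2). The variances of the three differences are 2(1−ρ)σ² = 1.0σ², 0.4σ² and 1.0σ². A random-intercept model pools them to 0.8σ², which understates the variance of Visit 1 minus Screening. In simulation that test rejects about 2.1% of the time under no effect at nominal 1%, while the paired t-test stays at 1.0%.

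**The case against.** The best defence is that the sentence already contains a sound analysis. The own-control wording makes the t-tests paired. A plain t-test or rank test cannot adjust for baseline variables, so the adjusted estimate must come from the mixed model, where the patient is the obvious random effect. Mann-Whitney may be a slip for signed-rank. Both comparisons are defined in advance in Protocol section 2, and the error from an unpaired test is conservative.

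Much of this stands. A reader might infer that the sponsor intends an unpaired analysis throughout, or a mixed model with no patient effect. The documents do not support that: leaving a term unstated is not evidence that it will be left out. A reader might also infer that power will collapse. The documents do not support that either, because the loss depends on a correlation they do not give and is nil at zero.

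What remains is that the only rank test named does not fit the design, that no text elsewhere corrects it, and that neither the primary method nor the primary contrast is stated. Defining two comparisons in advance does not say which one carries the 1% test.

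**Conclusion.** The SAP sentence is wrong as written on the rank test and incomplete on the contrast. The mismatch and the unnamed contrast follow directly from the text and can be held with high confidence. The size of the power loss cannot: it assumes normal data, a two-sided 1% test, an SD of differences of 0.05 and a between-visit correlation chosen for illustration. It also arises only if Mann-Whitney is run as named and relied on. The open contrast costs at most a doubling of the nominal 1%, and only if either comparison could be claimed. It should be corrected before analysis. It does not undermine the sample size, which is sound for a paired test to within a patient (44 against an exact 45).

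**What to change.** Rewrite the analysis sentence along these lines:

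- **Primary analysis:** paired t-test on within-patient differences in R5-R20, the analysis on which 44 rests, or the Wilcoxon signed-rank test if the differences are clearly non-normal. This replaces the present t-test/Mann-Whitney wording.
- **Primary contrast:** one of the two comparisons in Protocol section 2, named by the sponsor, tested at 1% with sidedness stated. The other is reported separately as secondary.
- **Supportive analysis:** linear mixed model with visit as a fixed effect, an unstructured within-patient covariance (not a random intercept alone), and the sponsor's baseline variables retained and listed.
- **Time point:** the sponsor states which measurement time enters the primary contrast, given that the scheduled 3-hour values do not isolate either comparison. The measurement and dosing times in Protocol sections 4 and 8 must be reconciled so that the chosen value has a defined relation to the dose.

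Cost: N and data collection do not change. If signed-rank is used on differences that are in fact normal, power falls by about 2 points (roughly 87% against 89%). If the sponsor chooses a time point other than 3 hours, the maximal response argued for in section 8 is given up. The documents do not say at which time the 0.03 effect was assumed.
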